6.2.2 Non-responder Imputation Analysis

If assessment of vIGA-AD after baseline is missing, the subject will be considered as non-responder (for example, no vIGA-AD success in the analysis of vIGA-AD success). For the vIGA-AD score endpoints, subjects with missing baseline vIGA-AD score will be considered as non-

 Innovaderm Research ■■■	STATISTICAL ANALYSIS PLAN, Version 1.0
Protocol Number: ARQ-151-315	Sponsor: Arcutis Biotherapeutics, Inc.

responder for these endpoints only. That is, for the secondary efficacy endpoints of vIGA-AD score of clear (0) or almost clear (1), the post-baseline assessment at a specific visit will be established based on the vIGA-AD score at that visit only, regardless of the availability of the baseline vIGA-AD score.

Similar imputation method will be used for EASI-75 where subjects with missing baseline EASI total score will be considered as non-responder.

Subjects who discontinued early from study due to an AE or lack of efficacy will be considered as a non-responder for all pre-specified analysis visits (refer to Section 5.4) for which the subject's last dose day falls within analysis visit window or is prior to the start of the analysis visit window.

6.2.3 Tipping Point Analysis

As a sensitivity analysis to the multiple imputation analysis as described in Section 6.2.1 for the vIGA-AD success primary endpoint, a tipping point analysis will be performed in order to determine the inflection point at which the inference under the missing not at random (MNAR) assumption changes substantially.

The sensitivity analysis for the primary endpoint will be performed by using a specified sequence of shift parameters. The range of shift parameters to be included in this analysis are 0 to 2 by 0.2 for active and -2 to 0 by 0.2 for Vehicle. The values at which the results of the primary analysis are shifted from significant (i.e., $\alpha \leq 0.025$) to non-significant (i.e., $\alpha > 0.025$) will be determined.

Steps 1 and 3 of the analysis will be the same as for the multiple imputation analysis as described in Section 6.2.1. However, Step 2 of the analysis is where the shift parameters will be applied.

Imputed values for subjects who discontinue due to lack of efficacy or adverse event will be handled as described in Step 2 of Section 6.2.1 to ensure that these subjects are analyzed as non-responders at all visits on or after discontinuation of treatment.

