5.5 Derived Variables

All questionnaire scores will be derived by Biostatistics in the ADaM datasets using the formulas defined below, even if calculated scores are present in the EDC database. All pre-calculated scores will be ignored for analysis.

- With the following exception, vIGA-AD Success = vIGA-AD of ‘Clear’ (0) or ‘Almost Clear’ (1) plus at least a 2-grade improvement from Baseline. The exception is that for subjects who discontinued early from study due to an AE or lack of efficacy, the subject will be considered as not having a vIGA-AD success (for MI and non-responder imputation analyses) or missing (for observed case analyses) for all pre-specified analysis visits (refer to Section 5.4) for which the subject’s last dose day falls within analysis visit window or is prior to the start of the analysis visit window.
- Average weekly WI-NRS = Average weekly WI-NRS pruritus score will be calculated as the sum of the daily WI-NRS scores reported during a specific week (in a 7-day period; refer to Section 5.4) of the study divided by the number of days with non-missing scores for that week. A minimum of 4 days of observations are needed to calculate an average weekly WI-NRS pruritus score. Otherwise, the corresponding average weekly WI-NRS pruritus score will be considered missing.
- With the following exception, a WI-NRS success = achievement of a 4- point reduction in average weekly WI-NRS pruritus score compared to average weekly WI-NRS baseline, calculated only for the subjects with average weekly WI-NRS score of ≥ 4 at baseline. The exception is that for subjects who discontinued early from study due to an AE or lack of efficacy, the subject will be considered as not having a WI-NRS success (for MI and non-responder imputation analyses) or missing (for observed case analyses) for all pre-specified analysis visits (refer to Section 5.4) for which the subject’s last dose day falls within the analysis visit window or is prior to the start of the analysis visit window.
- EASI total score = $0.2 (E_h + I_h + Ex_h + L_h) A_h + 0.2 (E_u + I_u + Ex_u + L_u) A_u + 0.3 (E_t + I_t + Ex_t + L_t) A_t + 0.3 (E_l + I_l + Ex_l + L_l) A_l$

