6.2.1 Multiple Imputation

All subjects, regardless of completion status, will have available data assigned to the pre-specified analysis visit using the analysis windows defined in Section 5.4, including the last available data of subjects who prematurely withdraws from the study. To comply with the definition of the primary estimand (Section 12.1.1), for subjects who discontinue due to lack of efficacy or adverse event, efficacy data assigned to a pre-specified analysis visit will be removed from the source data used for the multiple imputation process if subject's last dose day falls within the analysis visit window or is prior to the start of the analysis visit window used to assign data to a pre-specified analysis visit. This procedure will ensure that the data collected on or after these specific intercurrent events are not used in the imputation process.

For the primary efficacy endpoint of vIGA-AD success at Week 4 and the secondary endpoint of vIGA-AD success at Week 4 among subjects with a 'Moderate' randomized vIGA-AD score, the primary analysis will impute missing values using a Predictive Mean Matching (PMM) sequential-regression multiple imputation model for the ITT population. This is a three-step process.

1. The first step is to understand the pattern of missingness. In order to perform the multiple imputation, a monotone missing pattern has to be achieved. For example, if there exist values for baseline and Week 4 visits, but missing values for the Week 1 or 2 visits, the Markov-Chain Monte-Carlo (MCMC) method will be used to impute the small amount of missing data that may be missing at the intermediate visits that is required to make the missing data pattern monotone before applying the multiple imputation algorithm. This method uses a non-informative Jeffreys prior to derive the posterior mode from the expectation-maximization (EM) algorithm as the starting values for the MCMC method. The MCMC method will use the seed 6457149. The vIGA-AD score will be treated as a continuous variable for this step and the model will include the vIGA-AD scores at baseline, Week 1, Week 2, and Week 4. To avoid values that could not be observed in practice, imputed values will be rounded to the nearest integer (Round=1 option in PROC MI) in the range of 0 to 4.

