To determine the number of multiply-imputed datasets to be created at this step, the proportion of datapoints with non-monotone pattern across all visits and subjects will first be derived as follows:

$$\frac{\text{number of non monotone visits accross all visits and subjects}}{\text{total number of expected visits accross all subjects}} * 100$$

 Innovaderm Research ■■■	STATISTICAL ANALYSIS PLAN, Version 1.0
Protocol Number: ARQ-151-315	Sponsor: Arcutis Biotherapeutics, Inc.

Then, the following table will be used:

Non-monotone Missing Data	Number of Imputed Datasets
$\leq 2\%$	1
$> 2\% \text{ to } \leq 5\%$	3
$> 5\%$	10

2. Once the monotone pattern is achieved, the next step is to implement the imputation algorithm. For this, the PMM regression method will be used. This method is particularly helpful if the normality assumption is violated. For subjects with complete data up to a particular visit, a PMM regression model will be fit that includes the outcome at that visit as the dependent variable and as independent variables, the treatment group, and vIGA-AD score outcomes at previous visits, using a seed of 482371. For other scales/questionnaires, the actual baseline vIGA score will also be included as an independent variable. This process will be repeated 25 times, resulting in a total of 25 to 250 complete analysis datasets, depending on the number of imputed monotone datasets that are required. The seed may be changed after unblinding in case of any issues with the imputation process, and it will be documented in the CSR if any change is required.
3. For each of the 25 to 250 completed datasets, the necessary derived variable will be computed as defined in Section 5.5 and analyzed using a CMH analysis, adjusted for the randomized vIGA-AD score for the primary efficacy endpoint. The treatment effect on the secondary efficacy endpoint dealing with vIGA-AD success in the vIGA-AD moderate ITT population will be assessed with an unstratified chi-square test. Results will be combined into one multiple imputation inference as follows:

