12 EFFICACY ANALYSIS

12.1 Primary Efficacy Endpoint Analysis

12.1.1 Primary Efficacy Endpoint and Estimand

The vIGA-AD is a static evaluation of qualitative overall AD severity. This global assessment scale is an ordinal scale with five severity grades (reported only in integers of 0 to 4). Each grade is defined by a distinct and clinically relevant morphologic description that minimizes inter-observer variability. vIGA-AD is evaluated for the entire body except the scalp, palms, and soles.

The primary efficacy endpoint is vIGA-AD success, defined as an vIGA-AD score of ‘clear’ (0) or ‘almost clear’ (1) plus at least a 2-grade improvement from Baseline at Week 4.

The primary estimand is described by the following attributes:

Population: Patients with Atopic Dermatitis

Endpoint: vIGA-AD success at Week 4

Intercurrent events: In the course of the 4-week randomized treatment period, subjects may be exposed to possible known or unknown intercurrent events that could possibly impact the estimates of the estimand, such as treatment discontinuation due to a specific adverse effect or perhaps a lack of effect. A composite strategy will be implemented that handles subjects who discontinue due to lack of efficacy or adverse event as missing not at random differently than all other subjects. That is, subjects who discontinue due to lack of efficacy or adverse event will be treated as non-responders for all pre-specified analysis visits (refer to Section 5.4) for which the subject’s last dose day falls within the analysis window or is prior to the start of the analysis window (refer to Section 5.5) while the “Treatment Policy Strategy” will be adopted for handling intercurrent events in this study other than discontinuation due to lack of efficacy or adverse event.

Population-level summary: ratio of the odds of achieving vIGA-AD success after 4 weeks of using roflumilast cream 0.05%, relative to the odds of success after 4 weeks using a matching vehicle cream in the ITT population.

The supportive population-level summary: the proportion difference between Roflumilast cream 0.05% and vehicle groups will be provided for the patients who achieve vIGA-AD success at week 4 in the ITT population.

 Innovaderm Research ■■■	STATISTICAL ANALYSIS PLAN, Version 1.0
Protocol Number: ARQ-151-315	Sponsor: Arcutis Biotherapeutics, Inc.

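### Does the tipping-point analysis need a written rule for fractional vIGA-AD scores before its result can be read?

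*SAP*

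**What the plan says.** SAP 6.2.3 sets the shift ranges: they "are 0 to 2 by 0.2 for active and -2 to 0 by 0.2 for Vehicle". Its output is the set of shifts at which the primary result stops being significant at 0.025. On placement it says "Step 2 of the analysis is where the shift parameters will be applied" and "Steps 1 and 3 of the analysis will be the same as for the multiple imputation analysis".

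Step 2 of SAP 6.2.1 is the predictive mean matching step ("the PMM regression method will be used"). It is fitted visit by visit on treatment and the earlier vIGA-AD scores. Step 3 passes the completed data to SAP 5.5, where success is clear or almost clear "plus at least a 2-grade improvement from Baseline". SAP 12.1.1 describes the scale as "reported only in integers of 0 to 4".

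The one rounding rule for vIGA-AD belongs to Step 1, the MCMC fill-in of intermittent gaps: "imputed values will be rounded to the nearest integer (Round=1 option in PROC MI) in the range of 0 to 4".

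SAP 6.2.2 adds a fixed alternative assumption: "If assessment of vIGA-AD after baseline is missing, the subject will be considered as non-responder". SAP 12.1.3 also plans observed-data analyses in the ITT and PP populations.

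**The concern.** A step of 0.2 does not fit a scale of whole grades. If the shift is added to a drawn score of 1, the result is 1.2, and SAP 5.5 has no entry for that value. The Step 1 rounding rule is applied before any shift, so read strictly it does not cover the case. The SAP also leaves open whether the shift goes on the predicted mean or on the drawn value, whether it applies at Weeks 1, 2 and 4 or only at Week 4, whether shifted values feed the next visit's model, and whether the two ranges are crossed.

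The size of the tipping shift is what the analysis reports, and it is the only graded departure from missing-at-random planned for the primary endpoint. If the same data could give 0.2 under one convention and 0.6 under another, a reader might misjudge how robust the result is.

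**Working it through.** **Plan's own figure.** The SAP states no expected tipping value, so there is none to reproduce. The planning rates used below do reproduce the stated power. With 217 vehicle at 0.22 and 433 active at 0.37, the pooled rate is (47.74 + 160.21)/650 = 0.320, the null SE is 0.0388 and the alternative SE is 0.0365. Then z = (0.15 − 2.241 × 0.0388)/0.0365 ≈ 1.73, which gives power of 95.8% against a stated figure above 90%.

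**Reading A: shift on the predicted mean before matching.** Matching then returns an observed donor score, a whole number from 0 to 4. No 1.2 arises, SAP 5.5 applies as written, and steps of 0.2 on a continuous predicted mean are reasonable. The text allows this reading but does not require it.

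**Reading B: shift added to the drawn Week 4 score.** Success needs a score of at most 1 and an improvement of at least 2.

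- Active, level 1: Moderate-baseline draws of 1 and Mild-baseline draws of 0 stop being successes.
- Active, level 2: Moderate-baseline draws of 0 also stop.
- Vehicle, level 1: Moderate-baseline draws of 2 and Mild-baseline draws of 1 become successes.
- Vehicle, level 2: Moderate-baseline draws of 3 and Mild-baseline draws of 2 also become successes.

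With level 0 (no change), that makes three patterns per arm. The grading rule sets only where each one starts:

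| Rule | Active level 1 | Active level 2 | Vehicle level 1 | Vehicle level 2 |
|---|---|---|---|---|
| Unrounded, at most 1 | 0.2 | 1.2 | −1.0 | −2.0 |
| Nearest integer | 0.6 | 1.6 | −0.6 | −1.6 |
| Rounded down | 1.0 | 2.0 | −0.2 | −1.2 |

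Crossing the arms gives 3 × 3 = 9 pattern pairs, the same nine under each rule. The end patterns at +2 and −2 also agree, so whether significance is lost anywhere in the ranges does not depend on which of these rules is used.

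**Does the rule change which patterns tip?** The illustration uses 433 and 217 subjects, 75% Moderate in both arms, 25 imputations, CMH by baseline severity and Wilson-Hilferty pooling. Donors come from the same arm and stratum, a simplification of the planned matching. The missing rates are assumptions; the documents give none. Of the 11 shifts, levels 0, 1 and 2 cover 1, 5 and 5 values (active) and 5, 5 and 1 (vehicle) unrounded, and 3, 5 and 3 in both arms with nearest-integer rounding. Pairs are written (active level, vehicle level).

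- *37% v 22%, 10% missing.* Active alone never tips. Vehicle alone tips at −2.0 unrounded and −1.6 rounded, level 2 in both. Equal and opposite shifts tip at 1.0 and 0.6, level 1 in both arms either way. The losing pairs are therefore (0,2), (1,1), (1,2), (2,1) and (2,2). Cells unrounded: 1×1 + 5×5 + 5×1 + 5×5 + 5×1 = 61. Cells rounded: 3×3 + 5×5 + 5×3 + 3×5 + 3×3 = 73. Both match the simulated counts out of 121.
- *37% v 22%, 15% missing.* Vehicle alone now tips at level 1, which adds (0,1): 61 + 1×5 = 66 and 73 + 3×5 = 88. Both match.
- *35% v 22%, 10% missing.* Each arm alone tips at level 1 (active 0.2 or 0.6, vehicle −1.0 or −0.6), so every pair but (0,0) loses: 121 − 1×5 = 116 and 121 − 3×3 = 112. Both match.

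In each case the same patterns lose significance under both rules. The cell counts and shift labels differ; the finding does not.

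**Balance between arms.** With equal and opposite shifts, the arms sit at different levels in 8 of 10 non-zero pairs unrounded, 8 of 10 rounding down, and 0 of 10 with nearest-integer rounding, the only rounding rule the SAP writes for vIGA-AD.

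**The case for a change.** The best case for a change is that a pre-specified robustness measure should not rest on a convention chosen while programming, and that 0.2 and 0.6 will look different to a reader. There is also one reading that does matter. If success is taken as a score of exactly 0 or 1, a vehicle success shifted from 1 to 0.8 becomes a failure, and at 37% v 22% with 10% missing the non-significant cells fall to 21 of 121, against 61 and 73. In addition, 6.2.3 cites Step 2 for the handling of AE and lack-of-efficacy discontinuations, and Step 2 contains no such rule.

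The missing detail stands. The exact-value reading does not carry weight: it makes a shift meant to help vehicle count against it, which defeats the purpose of the analysis, and an analyst would reject it on sight. Rounding down appears nowhere in the SAP. The stated purpose of the Step 1 rounding, to keep out values that could not be observed, applies equally to a shifted score, so nearest-integer rounding within 0 to 4 is the natural extension. The wrong pointer is a clerical slip, since the rule is in the opening paragraph of 6.2.1 and in 5.5. Replacing the method with a grid of success probabilities or log-odds would be a preference; nothing shows the planned method to be invalid.

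**Conclusion.** No change to the plan is needed. The SAP names the step at which the shift enters but not its position within that step, the visits shifted, carry-forward or crossing of the ranges. These are programming details of one sensitivity analysis. Placed before matching, the shift produces no fractional score. Placed after it at Week 4, the sensible conventions move the label of the first active change between 0.2 and 0.6 but leave the nine pattern pairs, and which of them lose significance, unchanged. A footnote stating the convention lets a reader convert one label to the other.

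The primary p-value is unaffected. The group being shifted is also limited: discontinuations for AE or lack of efficacy stay non-responders, and the Week 4 window (Day 23 to 43, SAP 5.4) accepts early-termination data. Non-responder and observed-data analyses stand beside this one.

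The pattern counts are exact for a post-draw shift at Week 4 only and do not cover a shift at every visit. The significance results also rest on the assumed missing rates and simplified donor matching.

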6.3 Interim Analysis

No interim analysis is planned for this study.

6.4 Multicenter Studies

[figure not shown]
The study will be conducted at approximately 111 study sites in the US, Canada and Poland. During the conduct of the study, additional countries and/or sites may be added if necessary. Given the large number of sites, analyses will not be stratified by study site.

 Innovaderm Research ■■■	STATISTICAL ANALYSIS PLAN, Version 1.0
Protocol Number: ARQ-151-315	Sponsor: Arcutis Biotherapeutics, Inc.

6.5 Multiple Comparisons/Multiplicity

To control for familywise type I error at level of 0.025, the secondary efficacy endpoints will be tested sequentially at an alpha level of 0.025 upon successful demonstration of statistical significance for the primary endpoint. The order of the secondary efficacy endpoints is important. Should, anywhere during the sequential testing of secondary efficacy endpoints, there is a p-value >0.025 , further testing results are considered “not statistically significant” regardless of the p-value computed.

Figure 2 Multiple Testing Scheme

Achievement of vIGA-AD success is a score of “clear” or “almost clear” plus a 2-grade improvement from baseline.

EASI-75: achievement of at least a 75% reduction in the Eczema Area and Severity Index

6.6 Examination of Subgroups

Subset analysis for the following subgroups will be performed for the primary, secondary and WI-NRS success efficacy endpoints:

- Gender (male vs. female),
- Race (White vs. Black or African American vs. Asian vs. other),
- Ethnicity (Hispanic vs. Non-Hispanic),
- Randomized vIGA-AD score (mild (2) vs. moderate (3)),
- Actual baseline vIGA-AD score (mild (2) vs. moderate (3)),

 Innovaderm Research ■■■	STATISTICAL ANALYSIS PLAN, Version 1.0
Protocol Number: ARQ-151-315	Sponsor: Arcutis Biotherapeutics, Inc.

- Baseline % BSA (<10% vs. \geq 10%),
- %BSA categories based on tertiles,
- Baseline EASI total score (\leq 7 vs $>$ 7),
- Baseline EASI total score based on tertiles
- Fitzpatrick skin type at Screening (Type I, II and III vs. Type IV, V, and VI),
- Prior inadequate response, intolerance, or contraindication to Topical Corticosteroids (yes vs. no),
- Facial Involvement (yes vs. no)

For subgroup based on tertiles, tertiles will be derived using pooled data from both treatment groups based on the ITT population.

Details on these analyses are described in Section [12.4](#).

7 STUDY SUBJECTS

7.1 Disposition of Subjects

All subjects who provide informed consent will be accounted for in this study. The number of subjects who were screened and who failed screening (screen failures) will be presented. The reasons for screen failure will be presented for all screened subjects who failed screening.

The number of subjects randomized will be presented by treatment group. The number and percentage of the subjects included in each analysis population will be provided by treatment group. The number and percentage of the subjects who completed the study, who discontinued the study, the reasons for study discontinuation, and early termination due to COVID-19 disruption will be presented by treatment group. The percentages will be calculated using the number of the randomized subjects as denominator.

Number of days in the study will be summarized with descriptive statistics by treatment group and overall. For each subject, the number of days in the study will be calculated as following:

$$\text{Number of days in study} = \text{Date of completion/discontinuation} - \text{1}^{\text{st}} \text{ dose date}^* + 1$$

* For randomized subjects who discontinued study before the first application of study treatment, the date of randomization will be considered instead of the date of the first application of study treatment.

 Innovaderm Research ■■■	STATISTICAL ANALYSIS PLAN, Version 1.0
Protocol Number: ARQ-151-315	Sponsor: Arcutis Biotherapeutics, Inc.

A listing of subject's disposition and randomization will be provided. Information on first screening for subjects who were rescreened, including the rescreened subject identifier and the reason for first screening failure, will be presented under the first screening subject identifier. The reason for screening failure will be listed as well.

A table of randomized strata vs. actual strata will be provided if there is any mis-randomization discrepancy.

7.2 Protocol Deviations

A data review will be conducted before database lock by the Medical Monitor and the Sponsor to classify protocol deviations as minor or major.

The number and percentage of subjects with at least one important protocol deviation (including important protocol deviations associated with COVID-19) will be summarized by deviation category and treatment group using the ITT analysis set.

A listing of all protocol deviations will also be provided. The protocol deviations associated with COVID-19 and major PDs will be flagged.

